## D. Executive summary

#### Type of Study:

This is a prospective study, the goal of which is to validate the accuracy of the BiliSpec device in measuring bilirubin levels in neonates relative to the laboratory spectrophotometric bilirubinometer and transcutaneous bilirubinometer measurements.

## Problem:

Neonatal jaundice affects approximately 24 million newborns each year. If left untreated, severe jaundice can result in brain damage (kernicterus); while kernicterus is preventable, it is not treatable (1). Severe jaundice may not present until several days after birth, thus early monitoring of serum bilirubin levels is critical, particularly in premature babies who are more likely to suffer from jaundice and who are at greater risk of death and disability due to jaundice. In high-resource settings, tools to measure serum bilirubin levels are readily available and have made neurological damage from jaundice exceedingly rare; these tools have proven too expensive and complex to implement widely in under-resourced settings (2, 3). As a result, jaundice is diagnosed clinically in most low-resource settings using visual inspection of scleral yellowing; results are subjective and poor accuracy has been reported.

Recently, a team of researchers at Rice University in partnership with clinicians at Queen Elizabeth Central Hospital created BiliSpec, a low-cost battery-powered reader designed to immediately quantify serum bilirubin levels from a small drop of whole blood applied to a lateral flow strip. The simple and affordable BiliSpec system offers a faster and more cost-effective means to detect neonatal jaundice in under-resourced clinics and determine when phototherapy is needed. In 2017, a small 100 patient pilot study was performed at Queen Elizabeth Central Hospital in Blantyre, Malawi (Appendix 3). Results showed BiliSpec has comparable accuracy to laboratory standard and outperforms transcutaneous measurement of bilirubin (4).

#### Objectives:

The purpose of this study is to validate the accuracy of BiliSpec in comparison to laboratory standard spectrophotometric and transcutaneous measurement of bilirubin levels in neonates at two central hospitals: Queen Elizabeth Central Hospital in Blantyre, Malawi and Kamuzu Central Hospital in Lilongwe, Malawi.

#### Methodology:

We will recruit up to 500 neonates at QECH and KCH each, for a total of up to 1000 neonates, at risk for jaundice based on clinical signs and symptoms or undergoing phototherapy for treatment

of jaundice. BiliSpec, laboratory standard spectrophotometric measurement, transcutaneous measurement will be used to analyze bilirubin levels in both male and female babies with no preference towards a specific gender. Informed consent will be requested from the parents of all eligible babies on the ward for this study (Consent Forms in Appendix 1). If the guardian does not consent, the patient's bilirubin levels will be assessed using the standard of care on the ward. All eligible participants with consenting guardians will have their blood drawn via heel stick and measured with the three methods: BiliSpec, a commercially available spectrophotometric bilirubinometer according to standard laboratory practices, and a commercially available transcutaneous bilirubinometer. BiliSpec, the spectrophotometric bilirubinometer (Reichert UNISTAT® Bilirubinometer), the transcutaneous bilirubinometer, and accompanying equipment will be provided by the Rice study team. The Data Collection Form is found in the Appendix 2.)

#### **Expected Findings:**

We expect to find BiliSpec accurate and easy to use.

[figure not shown]
#### **Dissemination:**

[figure not shown]
The results of this study will be made available to the Ministry of Health, COMREC, the College of Medicine Library, the Department of Paediatrics at QECH and KCH, and other partners working in neonatal and child health. A copy of the final report and any published papers or abstracts will be submitted to The Health Sciences Research Committee and the University Research and Publication Committee (URPC) through the COMREC Secretariat. Findings will be published in academic journals and conference proceedings in an effort to disseminate results to potential end-users. The research findings of this study will be critical in the evaluation of future interventions.

## E. Literature Review and Background Information

Neonatal jaundice accounts for 114,000 infant deaths globally, with 85,500 of those deaths occurring in sub-Saharan Africa or South Asia. A further 180,000 neonates suffer permanent neurological damage every year from jaundice. Jaundice occurs when excess bilirubin builds up in the blood, and it is an especially common condition in premature babies, who lack sufficient liver function to excrete the excess bilirubin produced when fetal hemoglobin is broken down. Preterm babies also have a more permeable blood-brain barrier, which increases their risk of

kernicterus by allowing unconjugated bilirubin easier access to brain tissue. Neonatal sepsis and Rhesus incompatibility also increase the risk of jaundice. Fortunately, the complications of neonatal jaundice can be prevented through the use of phototherapy which has been highly successful in well-resourced hospitals (5). Bilirubin absorbs blue light, and phototherapy using blue light can be used to photodecompose bilirubin to a form that can be excreted. Laboratory determination of serum bilirubin concentration is vital in managing babies who are jaundiced. However, current methods of measuring total bilirubin are not feasible for district and health center laboratories. The standard for many hospitals is the diazo method for determining bilirubin levels in the patients. The diazo method requires many reagents, highly trained personnel, and a fully equipped laboratory to perform; all of which make implementation at the district level

Blood with Normal Bilirubin Levels

Blood with Elevated Bilirubin Levels

Figure 1. (a) Photograph of disposable lateral flow cards for blood collection. (b) BiliSpec Reader for measuring bilirubin

infeasible. Spectrophotometric determination of bilirubin requires no reagents, but requires both a centrifuge and a calibrated spectrophotometer, tools that cost thousands of dollars and are often not available in district hospital or health center laboratories. Transcutaneous measurement of bilirubin requires hardware and calibration consumables that are not affordable in many low-resource settings; accuracy of these devices is worse for neonates with dark skin and decreases during phototherapy (3, 6, 7).

In response to this need for early bilirubin monitoring, researchers at Rice University created BiliSpec, a low-cost battery-powered reader designed to immediately quantify serum bilirubin levels from a small drop of whole blood applied to a lateral flow strip. BiliSpec has two components: (1) an inexpensive, disposable lateral-flow strip on which the clinician spots a drop of whole blood from a heel prick and (2) a battery powered reader which measures the light transmitted through the serum on the detection strip and displays a digital report of the bilirubin concentration (Figure 1).

BiliSpec has been evaluated in the laboratory and in a small pilot study (Appendix 3) at QECH to test efficacy and usability (4). The BiliSpec lateral flow strip is capable of handling a range of blood volume to account for variations in volume from heel sticks. Full separation of plasma on the lateral flow strip takes approximately 1-2 minutes. In this time, the lateral flow device is sealed by the user after application of blood to prevent contamination or leaking. Measurement of bilirubin using BiliSpec during the pilot study yielded an average absolute difference of 0.8 mg/dL (95% CI of -1.7-2.2 mg/dL) as compared to the laboratory spectrophotometric measurement. The lateral flow strip costs less than \$0.05 and we estimate the reader can be built for less \$200 at low volume. We are optimizing BiliSpec to achieve a target accuracy of ±20% or 0.4mg/dL, whichever is greater (United States CLIA Standard) with a dynamic range up to 35 mg/dL, consistent with performance of bilirubin measurement techniques used in high-resource settings (3). During the pilot study, 95% of samples were within CLIA guidelines, and simple changes are expected to improve performance. One limitation of the pilot study was the limited range of bilirubin concentrations tested; during the validation study, we will increase the number of neonates tested to increase the number of samples at high bilirubin concentrations. We believe that rapid adoption of this technology is possible since BiliSpec is affordable and simple to use at the bedside.

BiliSpec provides an important tool to monitor the efficacy and progress of phototherapy, ensuring appropriate treatment dosage and duration. Used together, BiliSpec and blue light phototherapy have the potential to reduce the morbidity and mortality associated with neonatal jaundice.

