## [v] Sample Size

We will recruit a total of up to 1000 neonates at risk for jaundice based on clinical signs and symptoms.

During our pilot study, we evaluated 100 participants and collected 147 samples total. However only 7 samples collected were over 20 mg/dL. In addition to confirming the accuracy of BiliSpec in this validation study, we also want to ensure we have enough samples of clinically high bilirubin concentrations (>20mg/dL) to ensure our device functions properly over our intended dynamic range (0-35 mg/dL). To accomplish this, we will collect data from up to 500 participants at each location. Previous data have determined that the standard deviation of the difference between the Bilirubinometer and our device is 1.0 mg/dL. In order to detect a statistical difference between the Bilirubinometer and our device of 0.8 mg/dL, our target accuracy, at a statistical power of 90% and  $\alpha$  of 0.05 using a paired test, we need 34 samples (8). Since only 7 samples out of 100 participants during our pilot study were over 20 mg/dL, we will need up to 500

participants at each location to acquire the statistically significant number of samples over 20 mg/dL. The larger sample sizes will also us to conclusively validate the accuracy of the BiliSpec system over the full dynamic range of clinically relevant bilirubin concentrations.

In summary, 300 samples at each location are needed to show that the accuracy of BiliSpec is within 0.2 mg/dL of the laboratory standard spectrophotometric measurement (95% power, assuming 0.98 standard deviation of difference based on the pilot study); we have increased the number to up to 500 patients per location (1000 total) to increase the chances of recruiting patients over the full clinically encountered range of bilirubin concentrations, particularly at high concentrations.

This study will enroll up to 500 neonates at Queen Elizabeth Central Hospital and 500 neonates at Kamuzu Central Hospital who are deemed to be at risk for jaundice or who are receiving blue light phototherapy treatment for jaundice. We will compare the detection of bilirubin levels by BiliSpec to bilirubin monitoring with laboratory spectrophotometric bilirubinometry and transcutaneous bilirubinometry, the standard of care in developed settings.

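### The pilot interval of -1.7 to 2.2 mg/dL cannot be a confidence interval for a mean absolute difference, and the 0.8 and 0.2 mg/dL sample-size figures do not say which measure, or what bias, they assume

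*Combined protocol and SAP*

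**What the plan says.** Section E reports that the pilot comparison with the laboratory bilirubinometer "yielded an average absolute difference of 0.8 mg/dL (95% CI of -1.7-2.2 mg/dL) as compared to the laboratory spectrophotometric measurement". The same paragraph gives the accuracy being aimed for as the larger of 20% and 0.4 mg/dL.

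Section H[v] says of the pilot that "we evaluated 100 participants and collected 147 samples total", and then gives two calculations. The first takes it that "the standard deviation of the difference between the Bilirubinometer and our device is 1.0 mg/dL" and is set up as a paired test: "In order to detect a statistical difference between the Bilirubinometer and our device of 0.8 mg/dL, our target accuracy". The second states that "300 samples at each location are needed to show that the accuracy of BiliSpec is within 0.2 mg/dL of the laboratory standard spectrophotometric measurement", with 95% power and an SD of the difference of 0.98 from the pilot.

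Neither section gives the pilot's signed mean difference. H[v] does not say what true mean difference the second calculation assumes.

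**The concern.** An average of absolute differences is at least zero, so its confidence interval cannot reach -1.7. Either the measure or the interval is mislabelled, in the one sentence that summarises the pilot's accuracy.

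The labels matter because three measures of agreement are in play. The signed mean difference (bias) shows whether the device reads high or low on average. The limits of agreement show how far single readings stray. The mean absolute difference mixes the two. A device with no bias and an SD of about 1 has a mean absolute difference of about 0.8, whereas a device with a signed bias of 0.8 is systematically off. H[v] uses 0.8 in the second sense and Section E uses it in the first.

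Accuracy is the study's specific aim. The chance of supporting the 0.2 mg/dL statement depends on the true bias, which is the quantity that the pilot summary leaves unclear.

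**Working it through.** **Inputs.** From Section E: 0.8 mg/dL, and -1.7 to 2.2 mg/dL. From H[v]: 147 samples from 100 infants; SD of the difference 1.0 and 0.98; margin 0.2 mg/dL; 300 per site; 95% power. Alpha is not stated for the second calculation; 0.05 is assumed. Samples are treated as independent.

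**1. The plan's own power figure.** Standard error at n = 300: 0.98/√300 = 0.0566. With two one-sided tests at 0.05 each, a mean difference within ±0.2 is shown when the observed mean lies within 0.2 - 1.645 × 0.0566 = 0.107 of zero. At zero true bias the probability is 2Φ(0.107/0.0566) - 1 = 94%. The stated 95% is reproduced closely (exactly 95% needs 313).

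**2. Can the interval be a CI for a mean?** Its half-width is (2.2 + 1.7)/2 = 1.95. With SD 0.98, the half-width of a CI for the mean would be 1.96 × 0.98/√147 = 0.16, or 0.19 with n = 100. A half-width of 1.95 would need an SD of about 10 (n = 100) to 12 (n = 147).

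**3. What it does fit.** As mean ± 1.96 SD of the signed difference:
- SD = 1.95/1.96 = 0.995 (0.97 to 1.02 allowing for rounding of the limits), matching 0.98 and 1.0.
- Centre = (-1.7 + 2.2)/2 = +0.25 (0.20 to 0.30 from rounding).
- If 0.8 were the signed mean, the limits would be 0.8 ± 1.96 × 0.98 = -1.1 to 2.7, which does not match.

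The sampling 95% CI for that bias is 0.25 ± 0.16 = 0.09 to 0.41 with 147 independent samples, or 0.06 to 0.44 with n = 100. The positive sign assumes BiliSpec minus reference.

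**4. What the 0.8 is.** For normal differences with mean m and SD s, the mean absolute difference is s√(2/π) exp(-m²/2s²) + m[1 - 2Φ(-m/s)].
- m = 0: 0.78 (s = 0.98) or 0.80 (s = 1.0).
- m = 0.25, s = 0.98: 0.81.
- m = 0.8, s = 1.0: 1.04.

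So the pilot's 0.8 is what the scatter alone produces, and it cannot separate a bias of 0.25 from none. A signed difference of 0.8, as in the paired test, would be a different level of performance.

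**5. Power for the 0.2 statement when the bias is not zero** (two one-sided tests at 0.05 each, SD 0.98):

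| True bias (mg/dL) | n = 300 | n = 500 |
|---|---|---|
| 0 | 94% | over 99% |
| 0.05 | 84% | 96% |
| 0.10 | 55% | 74% |
| 0.15 | 22% | 31% |
| 0.25 | 0.6% | 0.3% |

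Pooling both sites (n = 1000) gives 94% at a bias of 0.10 and 0.06% at 0.25. With 0.025 per side, n = 300 gives 88%, 42% and 0.2% at biases of 0, 0.10 and 0.25.

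**The case against.** A reader might infer that the pilot bias already exceeds 0.2 mg/dL and that the trial is bound to miss its accuracy statement. The documents do not support that, for these reasons:

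- **The +0.25 is inferred.** It rests on rounded limits assumed to be symmetric. If they are percentiles, the midpoint need not be the mean. Rounding allows 0.20, and the sampling CI includes values well below 0.2. At a bias of 0.09, the lower end, power at n = 300 is about 62%.
- **The device has changed.** Sections E and F describe improvements after the pilot, so its bias need not carry over.
- **No test is named for the 0.2 figure.** A two-sided test to detect a difference of 0.2 also has 94% power at n = 300: Φ(0.2/0.0566 - 1.96). On that reading a bias of 0.25 would be detected with about 99% power, and the 0.6% does not apply. The wording about showing accuracy within 0.2 points to equivalence, but that remains a reading.
- **No pass or fail rule exists.** H[vii] (Data Analysis) says only that measurements will be compared.

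A reader might also infer that the 0.8 target was taken from the pilot's mean absolute difference. H[v] does not say so; only the figures coincide. The pilot's signed bias may be given in Appendix 3 or the cited pilot publication, neither of which was available here. Enrolment is driven mainly by the need for samples above 20 mg/dL.

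These objections make the bias and the power loss conditional. They do not rescue the interval's label, the use of 0.8 for two measures, or the unstated zero-bias assumption.

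**Conclusion.** Wrong as written, and worth correcting, though not serious enough to hold up the study. Three things stand.

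1. The interval in Section E cannot belong to an average absolute difference. It fits 95% limits of agreement with an SD of about 0.99.
2. The 0.8 mg/dL in Section E and the 0.8 mg/dL in H[v] are different measures. The target accuracy in H[v] also differs from the one in Section E (20% or 0.4 mg/dL, whichever is larger).
3. Read as an equivalence claim, the 95% power for 0.2 mg/dL assumes a true mean difference of zero without saying so.

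The size of the third depends on the bias of the improved device, which is unknown: at 300 per site, power runs from 94% at zero bias to 55% at 0.10 and 0.6% at 0.25. These figures assume two one-sided tests at 0.05, SD 0.98 and independent samples. The pilot value of about +0.25 further assumes symmetric limits.

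**What to change.** **Section E.** Check the pilot data and report three separately named measures: the signed mean difference with its own CI, the 95% limits of agreement, and the mean absolute difference. Define the direction of the difference.

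**Section H[v].** Say that the 0.8 and 0.2 mg/dL figures refer to the signed mean difference. Do not equate the 0.8 with the pilot's mean absolute difference, and reconcile it with the target accuracy in Section E. Name the test and alpha behind the 0.2 calculation. State that its 95% power assumes zero bias, and either show power for biases up to the pilot value or restate the 0.2 claim.

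**Cost.** Wording in two sections, plus a look back at pilot data. The stated power or the 0.2 mg/dL claim becomes less favourable. No added infants or data collection.

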#### F. Rationale/Justification for the research project

Neonatal jaundice affects approximately 24 million newborns each year. Unfortunately, bilirubin monitoring systems used in the developed world are too expensive for low-resource settings; instead, nurses and doctors often must visually monitor babies to watch for possible development of jaundice based on yellowing of the sclera. This method has been shown to lack sufficient accuracy. Also, in this geographical setting, there are few pediatricians, and nurses often staff many babies at a time. The poor predictive ability of visual diagnosis and the high ratio of babies to nurses and doctors means that cases of jaundice are often not identified early enough, resulting in brain damage or death. This challenge is prevalent in district hospitals throughout Malawi. A more consistent, low-cost method of jaundice diagnosis and monitoring is needed. Based on the results of the pilot study, BiliSpec may meet this goal. It is now necessary to validate performance of the improved BiliSpec device in a larger population of neonates with a larger range of bilirubin concentrations.

#### **G.** Objectives of the study

[i] Broad

The objective of this work is to validate the accuracy and usability of a new point-of-care device called BiliSpec to measure bilirubin concentration in neonates in low-resource settings.

## [ii] Specific

The specific aim of this study is to determine the accuracy of the BiliSpec device relative to a laboratory spectrophotometric bilirubinometer and transcutaneous bilirubinometer in the neonatal wards of Queen Elizabeth Central Hospital (QECH) and Kamuzu Central Hospital (KCH).

## H. Methodology

## [i] Study Type

This is a prospective study, the goal of which is to validate the accuracy of the BiliSpec device in measuring bilirubin levels in neonates relative to the laboratory spectrophotometric bilirubinometer and transcutaneous bilirubinometer measurements.

## [ii] Place of Study

The clinical study will take place at QECH in Blantyre, Malawi and KCH in Lilongwe, Malawi. Patients will be recruited from the neonatal wards at QECH and KCH who are deemed to be at risk for jaundice or are undergoing blue light phototherapy to treat jaundice.

## [iii] Study Population

Participants will be identified using the eligibility criteria stipulated below.

## Inclusion Criteria:

- 1. The patient is currently being treated at QECH or KCH in the neonatal ward.
- 2. The patient is less than 28 days old (neonate).
- 3. The patient is deemed to be at risk for jaundice or the patient is undergoing blue light phototherapy for treatment of jaundice.
- 4. The patient's parent or guardian has provided informed consent for their child to participate.

[figure not shown]
#### **Exclusion Criteria:**

- 1. Parent or guardian is unable or unwilling to provide informed consent.
- 2. The patient is unable to receive a blood draw/heel stick as determined by their clinician.

Families of neonates meeting eligibility criteria will be approached for consent to participate in the study by the investigator. If consent is not granted the patient will be treated with standard of care and will not participate in the study.

#### [iv] Study Period

Task	Start Date (month)	Duration (Months)	End Date (month)
Setup in QECH	0	0.5	0.5
Acquire up to 500 Samples from QECH	0.5	6	6.5
Setup in KCH	2	0.5	2.5
Acquire up to 500 Samples from KCH	2.5	6	8.5
Data Analysis	6.5	2.75	9.25
Compilation of Results	9.25	0.75	10

## [v] Sample Size

We will recruit a total of up to 1000 neonates at risk for jaundice based on clinical signs and symptoms.

During our pilot study, we evaluated 100 participants and collected 147 samples total. However only 7 samples collected were over 20 mg/dL. In addition to confirming the accuracy of BiliSpec in this validation study, we also want to ensure we have enough samples of clinically high bilirubin concentrations (>20mg/dL) to ensure our device functions properly over our intended dynamic range (0-35 mg/dL). To accomplish this, we will collect data from up to 500 participants at each location. Previous data have determined that the standard deviation of the difference between the Bilirubinometer and our device is 1.0 mg/dL. In order to detect a statistical difference between the Bilirubinometer and our device of 0.8 mg/dL, our target accuracy, at a statistical power of 90% and  $\alpha$  of 0.05 using a paired test, we need 34 samples (8). Since only 7 samples out of 100 participants during our pilot study were over 20 mg/dL, we will need up to 500

participants at each location to acquire the statistically significant number of samples over 20 mg/dL. The larger sample sizes will also us to conclusively validate the accuracy of the BiliSpec system over the full dynamic range of clinically relevant bilirubin concentrations.

In summary, 300 samples at each location are needed to show that the accuracy of BiliSpec is within 0.2 mg/dL of the laboratory standard spectrophotometric measurement (95% power, assuming 0.98 standard deviation of difference based on the pilot study); we have increased the number to up to 500 patients per location (1000 total) to increase the chances of recruiting patients over the full clinically encountered range of bilirubin concentrations, particularly at high concentrations.

This study will enroll up to 500 neonates at Queen Elizabeth Central Hospital and 500 neonates at Kamuzu Central Hospital who are deemed to be at risk for jaundice or who are receiving blue light phototherapy treatment for jaundice. We will compare the detection of bilirubin levels by BiliSpec to bilirubin monitoring with laboratory spectrophotometric bilirubinometry and transcutaneous bilirubinometry, the standard of care in developed settings.

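### The power for readings above 20 mg/dL is unverified: the 34-sample figure rests on an SD drawn almost wholly from lower readings, and its fixed 0.8 mg/dL target conflicts with the plan's ±20% target

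*Combined protocol and SAP*

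**What the plan says.** Section H [v] (Sample Size) uses a single SD: "Previous data have determined that the standard deviation of the difference between the Bilirubinometer and our device is 1.0 mg/dL". The next paragraph but one gives nearly the same value for a second calculation: "95% power, assuming 0.98 standard deviation of difference based on the pilot study". The aim of the first calculation is worded as "In order to detect a statistical difference between the Bilirubinometer and our device of 0.8 mg/dL, our target accuracy", with 90% power, alpha 0.05 and a paired test, and the answer is 34 samples. The section then applies the 34 to readings above 20 mg/dL. Because "only 7 samples collected were over 20 mg/dL" in the pilot (147 samples from 100 participants), it asks for up to 500 participants at each site.

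Section E (Literature Review and Background Information) states a different accuracy goal: "target accuracy of ±20% or 0.4mg/dL, whichever is greater". It reports that in the pilot "95% of samples were within CLIA guidelines", and it names the narrow range of pilot concentrations as a limitation.

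Section H [vii] (Data Analysis) says only that the measurements will be compared. It does not say whether differences are taken in mg/dL or in percent, or whether error is reported by concentration. No SD for any part of the range appears in the document.

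**The concern.** Good coverage above 20 mg/dL is the stated reason for going from 300 samples to as many as 500 patients per site. Yet the calculation for that range borrows its SD from the range the pilot did cover. If measurement error is larger at high bilirubin, 34 samples could fall short of 90% power where the plan most wants an answer. A fixed 0.8 mg/dL also does not test the plan's own standard, which at 20 mg/dL allows five times that amount (4 / 0.8 = 5). A reader of the results would not know which of the two targets BiliSpec had been sized, or judged, against.

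**Working it through.** **Inputs.** From H [v]: SD of the paired difference 1.0 mg/dL; difference 0.8 mg/dL; power 90%; alpha 0.05 (two-sided assumed, since sidedness is not stated); 147 pilot samples from 100 participants, 7 of them above 20 mg/dL. From E: target ±20% or 0.4 mg/dL; 95% of pilot samples within it; pilot interval −1.7 to 2.2 mg/dL. Not given: the SD above 20 mg/dL.

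**1. Is 1.0 the all-range pilot SD?** Read as limits of agreement, the pilot interval gives SD = (2.2 + 1.7) / (2 × 1.96) = 0.99, in line with 0.98 and 1.0. The share of pilot samples not above 20 is 140/147 = 95.2%.

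**2. The plan's 34.** With C = (1.960 + 1.282)² = 10.507:
- Paired, normal approximation: C × (1.0/0.8)² = 16.4. With the small-sample form C(s/d)² + 2 it is 18.4, and the exact noncentral t gives 19.
- Two independent groups: 1 + 2C(1.0/0.8)² = 33.8, so 34 per group.

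The stated paired test therefore needs 19. The 34 is reproduced only by the unpaired formula.

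**3. What the pooled SD says about the high range.** Ignoring differences in mean, 147 × 1.0² = 140 × s_low² + 7 × s_high².
- s_high = 1.4 gives s_low = √((147 − 13.72)/140) = 0.98.
- s_high = 2.0 gives √((147 − 28)/140) = 0.92.
- s_high = 3.0 gives √((147 − 63)/140) = 0.77.

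Seven samples in 147 barely move the pooled value, so it cannot tell these cases apart.

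**4. Number of samples expected above 20 mg/dL.** At 7 per 100 participants: 35 per site, 70 in total. At 7/147 per sample, with 500 samples per site: 24 per site, 48 in total.

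**5. Power for 0.8 mg/dL** (two-sided paired t, noncentral t), over assumed SDs above 20 mg/dL:

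| Pairs | SD 1.0 | 1.4 | 1.5 | 2.0 | 2.5 | SD at which power is 90% |
|---|---|---|---|---|---|---|
| 19 | 90.9% | 65.4% | 59.5% | 37.9% | 26.1% | 1.02 |
| 24 | 96.3% | 76.5% | 70.6% | 46.7% | 32.4% | 1.16 |
| 34 | 99.5% | 89.9% | 85.5% | 62.0% | 44.1% | 1.40 |
| 48 | 100.0% | 97.2% | 95.1% | 77.5% | 58.4% | 1.67 |
| 70 | 100.0% | 99.7% | 99.3% | 91.0% | 75.2% | 2.04 |

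**6. The ±20% scale.** The limit becomes proportional above 0.4/0.20 = 2 mg/dL and is 0.20 × 20 = 4 mg/dL at 20. If error were proportional and unbiased (an assumption), 95% within ±20% would mean a CV of 0.20/1.96 = 10.2%. Then 34 samples would give a 95% confidence interval for the mean percent difference of ±2.03 × 10.2/√34 = ±3.6 percentage points.

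**The case against.** The strongest reply is that nothing in the documents shows the SD rising. A reader might infer from the ±20% target, or from 95% of pilot samples meeting it, that error is proportional at about 10%. That would put the SD near 2.0 at 20 mg/dL (0.102 × 20) and near 3.6 at 35 (0.102 × 35), so that the claimed power is probably not delivered. The documents do not support that reading. A tolerance is an acceptance limit and says nothing about how error behaves. The 95% also fits a constant SD: with SD 1.0 and bias 0.25 (the midpoint of the pilot interval), the share within the limit is 67% at 5 mg/dL, 95% at 10 and 99.6% at 15. A 10.2% CV gives a pooled SD of 1.0 only if the root-mean-square pilot reading was about 1.0/0.102 = 9.8 mg/dL, and the pilot distribution is not given.

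It can also be said that 34 pairs are more than the stated test needs, so 90% is lost only when the SD above 20 passes 1.40, or about 2.04 if 70 samples are pooled over the sites. If the difference were scaled with the target, to 4 mg/dL at 20, power with 34 pairs would be essentially 100% even at SD 3.5. And the plan itself acknowledges the narrow pilot range and raises enrolment because of it.

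All of this stands against a claim that power is missing. It does not supply an SD for the high range or reconcile 0.8 mg/dL with ±20%. The slack in 34 comes from an unpaired formula: once corrected to 19, power is kept only up to SD 1.02. Nor does the plan say that the sites are pooled. It asks for 500 participants at each location, and the 35 samples expected per site closely match the 34.

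**Conclusion.** The point holds as a gap in justification. The 90% power above 20 mg/dL is unverified, because the SD comes about 95% from readings at or below 20, and the 0.8 mg/dL target conflicts with the target in section E. Taking 34 samples as planned, power for 0.8 mg/dL runs from 99.5% at SD 1.0 to 44% at SD 2.5; with 70 pooled, it stays above 90% up to an SD of about 2.0 and is 75% at 2.5. These figures assume a two-sided test and independent pairs, and the SDs above 1.0 are assumed values. Where the true SD lies in that range cannot be settled from the documents. Against ±20%, 34 samples look ample if the CV is near 10%, so choosing the scale matters more than adding patients.

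**What to change.** In H [v]:
- State one accuracy target for readings above 20 mg/dL and reconcile 0.8 mg/dL with ±20%.
- Correct the paired calculation (19 at the stated inputs) in the same edit, since changing it alone removes the slack.
- Preferably, base the high-range number on percent or log-ratio differences against ±20%, stating the precision that 34 samples give and the CV assumed. Otherwise keep mg/dL and state power for SDs from 1.0 to 2.5.
- In either case, say whether the two sites are pooled.

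In H [vii]:
- Analyse percent differences where ±20% exceeds 0.4 mg/dL, that is, above 2 mg/dL.
- Report bias and SD separately for readings at or below 20 and above 20 mg/dL.

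The cost is wording and slightly more analysis of measurements the study already plans to collect, with no extra enrolment. The downside is a less favourable power statement if the mg/dL scale is kept.
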